Colonoscopy in the prone position for patients with BMI >30 is superior to standard left lateral decubitus position

Protocol: IRB-HSR 20078

10/4/2017

Page 0 of 5 Version: 10-4-17

PROTOCOL

Background

1. Provide the scientific background, rationale and relevance of this project.

In the United States, colonoscopy has become the most commonly used screening test for colorectal cancer (7). Colonoscopy is typically performed with the patient starting in the left lateral decubitus position, however there is little data to support this practice. Throughout the colonoscopy, patients are often re-positioned in a variety of ways (shifted into a prone or supine position) to facilitate passage of the endoscope. There are a number of patient characteristics that are known to make colonoscopy more technically challenging necessitating positional changes, including female gender, prior abdominal or pelvic surgery, and BMI > 30. Despite these differences, there is minimal data in the literature to guide endoscopists regarding which patient positioning strategies to employ based on individual patient characteristics. It is estimated that 35% of adult men and 40.4% of adult women were identified during recent a recent study to fall into the "obese" category with BMI \geq 30 (8). Patient repositioning and application of pressure to the abdomen, another frequently used technique, can be particularly difficult for endoscopy staff to employ in a sedated, obese patient (9). The time from starting the colonoscopy until the colonoscope is advanced to the cecum, cecal intubaton time, is standardly recorded during colonoscopy. Longer cecal intubation times reflect more technically challenging procedures.

Several published studies investigating the Trendelenburg position (1) suggested decreased cecal intubation time, particularly in patients with significant sigmoid diverticulosis. However this technique revealed the increased occurrence of transient oxygen desaturation in obese patients which limited its use in this population. The right later decubitus position is frequently used to help advanced of the endoscope within the cecum or into the terminal ileum (2). In particular, women and patients who have previously undergone abdominal surgery seemed to benefit from right lateral decubitus position with improved cecal intubation times (4).

The prone position has been shown to successfully reduce ileal intubation times in a study involving 150 patients (3) regardless of BMI.

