- 2. Describe expected rate of screen failure/ dropouts/withdrawals from all sites. Expect 20% of screened patients will qualify and consent to participate in the study
- 3. How many subjects will be enrolled at all sites? 150
- 4. How many subjects will sign a consent form under this UVa protocol? 150

Inclusion/Exclusion Criteria

1. List the criteria for inclusion

- Willingness and ability to comply with scheduled visits and study procedures.
- BMI >30
- Undergoing screening or diagnostic colonoscopy at UVA as part of clinical care

Page 2 of 5 Version: 10-4-17

• Adults aged 18-90

2. List the criteria for exclusion

- Pregnant women (self reported).
- Cognitively impaired
- Hx colonic resection
- Cannot lay in prone position
- Hx of colon malignancy
- Procedure aborted due to bowel prep
- Severe pulmonary problems (baseline oxygen use)
- Inablility to consent

3. List any restrictions on use of other drugs or treatments.None

Statistical Considerations

1. Is stratification/randomization involved?

Yes – Randomization only

► IF YES, describe the stratification/ randomization scheme.

Study participants will be randomized to either left lateral decubitus or prone position at the time of colonoscopy. Randomization order will be computer generated with allocation concealment using sequentially numbered, sealed envelopes. Patients and co-investigators performing colonoscopy will not be blinded.

► IF YES, who will generate the randomization scheme?

____x_ Other: PI

2. What are the statistical considerations for the protocol?

-Prospective Randomized trial.

-Enrolled participants will be randomized to colonoscopy in the left lateral decubitus or prone position. -The primary endpoint is cecal intubation time. Cecal intubation time is standardly recorded during all colonoscopies. Null hypotheses is that there will be no difference in cecal intubation times between the 2 groups. To detect an effect size of 60 seconds difference between the 2 groups (left later decubitus vs prone position) with a standard deviation of 120 seconds for the average colonoscopy = ~125 total study participants - 63 per group (alpha = 0.05 / type I error rate). Type II error rare: 0.2. Goal to enroll 150 to adjust for variability in cecal intubation time.

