-Two secondary endpoints will be measured: complication rate in each group as well as sedation use. -Complications during the procedure will be noted and charts will be reviewed for complications occurring within 30 days of the procedure. Complications will be recorded as either present vs absent. -Sedation use is standardly recorded during all procedures. This is record as mg of fentanyl and mg of midazolam. Page 3 of 5 Version: 10-4-17

3. Provide a justification for the sample size used in this protocol.

To detect an effect size of 60 seconds difference between the 2 groups with a standard deviation of 120 seconds for the average colonoscopy = 125 total study participants - 63 per group (alpha = 0.05). Goal to enroll 150 to adjust for variability in cecal intubation time.

4. What is your plan for primary variable analysis?

T test for comparison of mean cecal intubation time in each group.

5. What is your plan for secondary variable analysis?

T test for comparison of mean amount of sedation used in each group as well as number of adverse events/ complications

6. Have you been working with a statistician in designing this protocol?No

7. Will data from multiple sites be combined during analysis? no

Study Procedures-Biomedical Research

1. What will be done in this protocol?

Patients that have been scheduled for colonoscopy will undergo chart review by the co-investigator (GI attening) scheduled to perform the colonoscopy or the GI fellow. Patients who meet inclusion criteria will be invited to participate at the time consent is obtained for the colonoscopy. Participants will then be randomized to one of two colonoscopy starting positions.

After randomization, patients will begin the colonoscopy in either the prone position or left lateral decubitus position.

Adjusting patient starting position to the prone rather than left lateral decubitus position is not expected to result in any additional risk to the patient beyond the standard risks related to colonoscopy. It is common practice to re-position the patient during endoscopy (including supine and prone positions) and some endoscopists commonly employ prone starting position for obese patients, although there is no estimate in the literature as to the prevalence of this practice.

No additional interventions will be performed for research purposes.

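### Several endoscopists perform the procedures, but the operator is left out of the primary analysis and prior prone-start experience is not recorded: adding both is a cheap improvement

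*Combined protocol and SAP*

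**What the plan says.** Under Statistical Considerations, item 2, "The primary endpoint is cecal intubation time". Item 1 describes computer-generated, unstratified randomisation in sealed envelopes, and adds: "Patients and co-investigators performing colonoscopy will not be blinded". The plural means more than one operator, and Study Procedures, item 1, has each patient's scheduled attending performing the procedure. The number of operators is not given.

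Item 4 gives the whole primary analysis: "T test for comparison of mean cecal intubation time in each group". Study Procedures lists cecal intubation time, sedation and intra-procedural complications as the data for analysis, drawn from the procedure report. Operator identity, operator experience and case order are not listed.

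On usual practice, the Background says: "Colonoscopy is typically performed with the patient starting in the left lateral decubitus position". Study Procedures adds that "some endoscopists commonly employ prone starting position for obese patients", says that the prevalence of this is unknown, and notes that moving patients during the procedure, including to prone, is common. No section describes the trial operators' own experience, or any training or run-in.

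**The concern.** The endpoint is the time an endoscopist takes to reach the cecum, so it reflects the operator as well as the patient and the starting position. Two things follow from leaving the operator out.

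The first is precision. If operators differ in speed, that variation stays in the error term of the t test. If by chance a faster operator has more patients in one arm, nothing corrects the estimate.

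The second is interpretation. The hypothesis is about the position itself. If the operators are practised at left lateral starts and less so at prone starts, any slowness from unfamiliarity falls on the prone arm only. Randomisation balances operators between arms in expectation, but it cannot balance a penalty that exists in one arm. A null or small difference could then mean that position does not matter or that prone starts were unfamiliar, and the planned data would offer no way to examine which.

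**Working it through.** **Inputs from the protocol (Statistical Considerations, items 2 and 3).** Difference 60 s, "with a standard deviation of 120 seconds for the average colonoscopy", alpha 0.05, type II error 0.2, 63 per group, enrolment goal 150 (75 per arm if equal).

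**Step 1: the plan's own figure.** n per arm = 2 × (1.960 + 0.842)² × 120² / 60² = 2 × 7.85 × 4 = 62.8, so 63 per arm and 126 in total. This matches the stated 63 and about 125, with a two-sided alpha; one-sided gives 50 and does not match. At 75 per arm, power for 60 s is 0.86. The calculation uses one SD and one common effect, with no operator component.

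**Step 2: precision of the planned t test.** Standard error = 120 × √(2/75) = 19.6 s. With 148 degrees of freedom, t = 1.976, so the 95% confidence interval half-width is 38.7 s.

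**Step 3: precision with an operator term.** The documents give no operator share of variance, so a range is assumed. Half-width = 38.7 × √(1 − share), and power ≈ Φ(60 / [120 × √(1 − share) × √(2/75)] − 1.96), both before the cost in step 4.

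| Assumed operator share | Residual SD (s) | Half-width (s) | Power for 60 s |
|---|---|---|---|
| 0% | 120.0 | 38.7 | 0.86 |
| 5% | 117.0 | 37.7 | 0.88 |
| 10% | 113.8 | 36.7 | 0.90 |
| 20% | 107.3 | 34.6 | 0.93 |
| 30% | 100.4 | 32.4 | 0.96 |

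**Step 4: the cost of the term.** Five operators as fixed effects add four parameters. The change in t is negligible (1.976 to 1.977). Because operators are not perfectly balanced between arms, the variance rises on average by about 4/148 = 2.7%, hence the half-width by about 1.35%: 38.7 × 0.0135 = 0.5 s. Break-even is an operator share of about 2.7%; below that, the fixed-effect model is slightly worse than the t test. With ten operators the same reasoning gives 38.7 × 9/(2 × 148) = 1.2 s, which is why low-volume operators should be pooled or a random intercept used.

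**Step 5: illustration of an unfamiliarity penalty.** Every input here is an assumption. If each operator's early prone cases run slow, the prone mean shifts by (operators × early cases / 75) × extra seconds.

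- Three operators, first 3 cases, 30 s: 9/75 × 30 = 3.6 s. A true 60 s benefit appears as 56.4 s; power 0.82.
- Five operators, first 5 cases, 60 s: 25/75 × 60 = 20 s. It appears as 40 s; power 0.53.

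These treat every operator as a learner, so they are too high if some already start patients prone. They show that the consequence could be negligible or substantial, and the documents do not favour either.

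**The case against.** An unadjusted t test in a randomised trial is legitimate. Operators are balanced in expectation, type I error is intact, and the result answers a real question: position as these operators deliver it. Unfamiliarity would work against prone, so it could not produce a false claim of prone superiority. Power at 75 per arm is already 0.86, and at a 5% to 10% operator share the gain is only 1 to 2 s. All of this stands, and it limits the point to an improvement.

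A reader might infer that this trial's operators have unequal prone experience, and that position is therefore confounded with skill. The documents do not support that. The remark about some endoscopists concerns endoscopists in general, and the same sentence calls repositioning during the procedure, including to prone, common practice. Working prone is thus not presented as new; only the prone start is less usual. Endoscopists may also change position as needed in either arm, which may limit any penalty. What survives does not require unequal experience: operators who were all unpractised would leave the same ambiguity, and nothing planned would reveal it.

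It can also be said that operator identity is probably recoverable, since the data come from procedure reports. That is likely, and it makes the change cheaper. It does not put the operator in the analysis, and prior prone use is absent altogether.

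**Conclusion.** This is a cheap improvement, not a flaw that invalidates the primary test. With an operator term, the half-width at 75 per arm falls from 38.7 s to between 37.7 s and 32.4 s if operators account for 5% to 30% of variance, less about 0.5 s with five operators as fixed effects. At a share near zero there is no gain and a loss of about 0.5 s. The operator share and the number of operators are assumptions.

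On interpretation, the conclusion is conditional: if the operators are less practised at prone starts, a null or reduced result would be hard to read. The tempting stronger statement, that the trial is biased against prone by a known amount, is not supported, because the documents give neither the operators' experience nor the size of any penalty. Nor would an operator term by itself separate unfamiliarity from position; it addresses precision and chance imbalance only.

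**What to change.** 1. Extract a coded identifier for the endoscopist performing each procedure, and specify before analysis that the primary comparison of cecal intubation time includes operator, as a random intercept or as a fixed effect with low-volume operators pooled by a stated rule.
2. Record once, before each operator's first enrolment, whether that operator regularly starts obese patients prone.
3. Report the position effect by prior prone use and by the order of each operator's prone cases in the trial, labelled exploratory. Word any null or small result as applying to operators with the experience observed.

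The cost is one coded field per procedure, one question per operator, a model in place of a plain t test, and a few degrees of freedom. No extra patients are needed and no procedure changes. At 150 patients the experience breakdown will describe the ambiguity but not resolve it.

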During the colonoscopy, the endoscopist will be allowed, as usual, to adjust patient position as needed to complete the procedure. Cecal intubation time, amount of sedation used, and any intra-procedural complications (hypoxia, hypotension, etc) will be recorded for data analysis. This information is standardly recorded in the procedure report in the patient's medical record. The study will not affect any interventions performed during the colonoscopy such as polyp removal or biopsies as, clinically indicated. Per endoscopy unit protocol, patients will be monitored in the recovery area and discharged home with supervision. The study requires no further direct patient interaction after the colonoscopy is completed. Charts will be reviewed at 30 days to assess for any delayed and unexpected complications.

Page 4 of 5 Version: 10-4-17

2. If this protocol involves study treatment, explain how a subject will be transitioned from study treatment when they have completed their participation in the study. N/A

Subject Compliance with Study Procedures

- 1. **Explain how the study team will monitor the subject for compliance with the study procedures.** Patient compliance is only requiring at the time of the colonoscopy. The performing endoscopist will note of patient is not able to comply with starting position per randomization.
- 2. Describe criteria for when a subject is considered to be non-compliant with study procedures. N/A

Bibliography

- 1) Colonoscopy in the tilt-down position Weinstock, Leonard B.Early, Dayna S. et al. Gastrointestinal Endoscopy , Volume 80 , Issue 4 , 746
- Achieving cecal intubation in the very difficult colon. Rex DK. Gastrointest Endosc. 2008 May;67(6):938-44. doi: 10.1016/j.gie.2007.12.028. Review.
- The prone 12 o'clock position reduces ileal intubation time during colonoscopy compared to the left lateral 6 o'clock (standard) position.
 De Silva AP, Kumarasena RS, Perera Keragala SD, Kalubowila U, Niriella M, Dassanayake AS,

Pathmeswaran A, de Silva HJ.

BMC Gastroenterol. 2011 Aug 4;11:89. doi: 10.1186/1471-230X-11-89.

- Right Or Left in COLonoscopy (ROLCOL)? A Randomized Controlled Trial of Right- versus Left-Sided Starting Position in Colonoscopy. Vergis N, McGrath AK, Stoddart CH, Hoare JM. Am J Gastroenterol. 2015 Nov;110(11):1576-81. doi: 10.1038/ajg.2015.298. Epub 2015 Sep 29.
- 5) Prone positioning of obese patients for colonoscopy results in shortened cecal intubation times: a randomized trial.

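### Hypoxia and hypotension feed a present/absent secondary endpoint with no measured criterion, and their only described source is the routine report of an unblinded procedure, so ascertainment could differ by arm.

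*Combined protocol and SAP*

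**What the plan says.** Statistical Considerations, item 2, names the endpoint: "Two secondary endpoints will be measured: complication rate in each group as well as sedation use". The scale is binary and ungraded: "Complications will be recorded as either present vs absent". The same item says that events during the procedure will be noted and that charts will be reviewed for events within 30 days.

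Study Procedures, item 1, describes the intra-procedural part: "any intra-procedural complications (hypoxia, hypotension, etc) will be recorded for data analysis". The source follows: "This information is standardly recorded in the procedure report in the patient's medical record". The later review has another purpose: "Charts will be reviewed at 30 days to assess for any delayed and unexpected complications". The same item states that nothing is added to routine care for research.

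On blinding, Statistical Considerations, item 1, is explicit: "Patients and co-investigators performing colonoscopy will not be blinded". The documents do not say who enters hypoxia or hypotension in the report, or whether the person who reviews the charts knows the assigned position.

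The Objectives section expects no difference in complications between positions. The Background says the earlier randomized study of prone positioning in obese patients reported no sedation or airway complications, and that prone positioning may lower the risk of obstructive apnea.

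**The concern.** Oxygen saturation and blood pressure are numerical measurements, but the plan gives no value, duration or reading schedule that turns a measurement into an event. The list of events is also left open. The primary endpoint is treated differently: the Background gives cecal intubation time a start and an end.

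With no criterion, whether a short, self-resolving dip counts may depend on what is judged worth entering in a report, by staff who may know the position. Blinding the operator to position is hardly practicable, so a fixed, measured definition is the main protection available for this endpoint. The Background shows that such events matter in this population. It describes "increased occurrence of transient oxygen desaturation in obese patients" as having limited another position (Trendelenburg, which is not a study arm), and this trial enrols only patients with BMI above 30.

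The complication comparison is at stake. If the share of true events that reach the report differs by arm, the comparison is biased, and a larger sample would not remove the bias. The expectation of no difference could then appear confirmed or refuted partly through reporting practice.

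**Working it through.** **The plan's own figure.** The documents give no expected rate, power or margin for complications. The only figure to reproduce is the primary-endpoint sample size: n per group = 2 × (1.960 + 0.842)² × (120/60)² = 62.8, rounded up to 63, or 126 in total. This agrees with the stated 63 per group and about 125 in total. It concerns cecal intubation time and has no bearing on the present point.

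**Inputs.**
- Patients per arm: 150/2 = 75 (enrolment target; equal allocation is implied by the equal group sizes).
- True event rate p, the same in both arms: assumed, 3% to 20%.
- Probability s that a true event reaches the report: assumed, 1.0 in one arm and 0.5 in the other.
- Test: two-sided Fisher exact test at 0.05, used for illustration. The plan names a t test on the number of complications.

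**Method.** Observed rate = p × s in each arm. The rejection probability is the sum of the binomial probabilities of all pairs of counts (0 to 75 in each arm) for which Fisher p ≤ 0.05.

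**Creating a difference (true rates equal).**

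| True rate, both arms | Observed rates | Expected reported events | P(significant), full vs half reporting | P(significant), full reporting in both |
|---|---|---|---|---|
| 20% | 20% vs 10% | 15 vs 7.5 | 0.32 | 0.03 |
| 10% | 10% vs 5% | 7.5 vs 3.75 | 0.13 | 0.03 |
| 5% | 5% vs 2.5% | 3.75 vs 1.9 | 0.04 | 0.015 |
| 3% | 3% vs 1.5% | 2.25 vs 1.1 | 0.009 | 0.006 |

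Milder differences in reporting matter less. At a true rate of 20%, full reporting against 80% gives 0.06, and 90% against 50% gives 0.22.

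The ratio of observed rates is 1.0/0.5 = 2 in every row, although the true ratio is 1. At low rates the distortion is therefore still in the estimates, but it seldom reaches significance.

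**Hiding a difference.** Suppose the true rates are 30% and 10%. Full reporting in both arms gives Fisher power of 0.84. If the higher-risk arm is reported with probability 0.5 and the other with 0.9, the observed rates are 15% and 9%, and power falls to 0.14.

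**Equal under-reporting.** With s = 0.8 in both arms and a true rate of 20%, the false-positive probability is 0.03, the same as with full reporting. The problem is a difference between arms. Incomplete reporting alone does not produce false signals.

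**The case against.** The strongest reply is that the text shows a missing definition and nothing more. Several parts of it stand.

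- **Sole source.** A reader might infer that these events count only if they appear in the procedure report. The documents do not say so. Complications are also to be noted during the procedure, and charts are reviewed to 30 days. What can be said is that the report is the only source described for intra-procedural hypoxia and hypotension, because the 30-day review is aimed at delayed and unexpected events.
- **Actual bias.** A reader might also infer that staff will watch prone patients more closely, or will leave out dips that resolve on repositioning. Nothing in the documents supports either habit. They also do not rule out a unit standard for what is entered.
- **Low risk.** The desaturation in the Background occurred in the Trendelenburg position. For prone positioning the Background points the other way, and patients on baseline oxygen are excluded. The true rate may therefore be low, which is why the table runs down to 3%.
- **Hidden harm at modest differences.** It is tempting to point to 12 of 75 against 6 of 75 being turned into 6 against 6. With perfect reporting, 12 against 6 gives Fisher p = 0.21, and power for 16% against 8% is about 0.25. Under-reporting would cost the point estimate there, but rarely a significant finding.
- **Secondary endpoint.** Cecal intubation time and sedation dose in mg are unaffected.

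These replies limit the size of the problem. They do not supply a criterion, a second described source or a blinded assessment for events that the plan intends to compare between arms.

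**Conclusion.** The point holds as a risk to one secondary endpoint. The plan compares complications between arms using a present/absent score. For hypoxia and hypotension that score has no measured criterion, and its only described source is the routine report of an unblinded procedure. Arm-dependent ascertainment is therefore possible and could bias the comparison in either direction. The documents do not establish that it will occur or how large it would be.

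The size depends on assumed rates and reporting probabilities. With full against half reporting, the chance of a false signal runs from 0.32 at a true rate of 20% to 0.009 at 3%. The larger figure needs both a common event and a severe imbalance in reporting, so it should not be quoted alone. At rates of about 5% or below, the practical harm is to the estimated rates and their ratio. The conclusion does not extend to the primary endpoint. The change is worth making because it is cheap and closes a gap that cannot be closed once the data have been reported selectively.

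**What to change.** For hypoxia and hypotension, take the data from the oximetry and blood-pressure readings in the routine sedation-monitoring record. The documents do not mention such a record, so the investigators should first confirm that it is kept and retrievable for both arms. Score each patient present or absent against one numeric threshold per event. The investigators choose the thresholds before the first patient, and the same rule applies in both arms.

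Report these threshold-based events separately from other complications, which stay with the procedure report and the 30-day chart review. Without that separation, minor dips could swamp serious events in a single present/absent score.

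The cost is a short protocol addition and some abstraction time per patient, with no added procedure. The downside is a higher count of minor events in both arms. If the investigators already intend to use the monitoring readings, stating that source and the thresholds is enough.
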